### **9.3.1. Benefit/Risk Balance**

I10E have been developed by LFB and manufactured from plasma pools which are EMA certified.

Marketing Authorization Application (MAA) was submitted in Intravenous Immunoglobulin (IVIg) Core Summary of Product Characteristics (SPC) indications through the Decentralized Procedure (DCP) in the following European Union Member States: Austria, Belgium, Czech Republic, Denmark, Finland, Germany, Greece, Hungary, Italy, Luxembourg, the Netherlands, Spain, Slovakia, Sweden, and the United Kingdom. The marketing authorization was obtained in the United Kingdom in August 2015, then in Denmark, Hungary, Germany, Belgium and Finland.

This study is designed according to the currently accepted scheme of the standard of care of CIDP, based on the clinical guideline (EFNS/PNS CIDP Guideline 2010, First revision) which is in line with European countries' recommendations and the recommendations of EMA. IVIg are used in CIDP patients and have shown a favorable benefit/risk balance. I10E has already been assessed in two pivotal studies: I10E-0718 and I10E-0719, respectively in PID and ITP, in 100 patients. Both studies concluded to a comparable safety profile with IVIg preparation. The I10E doses recommended in this protocol will not exceed those used in current medical practice in this indication, in the before-mentioned clinical trials. Participation in the study is not expected to induce significant additional risk for patients.

### **9.4. Alternative Therapeutic Management - Handling Emergencies**

- If allergic or anaphylactic-type reactions occur, the infusion must be stopped immediately and standard medical treatment must be implemented.
- In case of misuse and/or overdose, appropriate corrective actions should be promptly undertaken when possible. The patient should be followed-up until the assurance that no AE occurs is obtained.

### **9.5. Definition and Reporting of (Serious) Adverse Events**

#### **9.5.1. Definition of Adverse Event and Serious Adverse Event**

An AE is any untoward medical occurrence in a patient or clinical investigation subject to whom a medicinal product is administered. The occurrence does not have necessarily a causal relationship with the treatment. An AE can therefore be any unfavorable and unintended sign (including an abnormal laboratory finding, for example), any symptom or disease, whether new or exacerbated, temporally associated with the use of a medicinal product, whether or not related to the investigational drug product.

An AE, whether or not considered to be causally related to the investigational drug product, may be:

- The deterioration of a pre-existing chronic disease or aggravation of a symptom or disease that was present at inclusion of the patient in the study.
- A symptom or disease discovered after the start of the study even if it was probably present prior to the patient's inclusion.
- Abnormal laboratory findings when they are considered as clinically significant by the Investigator.

In case a vital sign shows a clinically significant abnormality, an AE should be reported (or the abnormal vital sign should be linked to an already reported AE). A serious AE is an AE that, at any time, fulfils one or more of the following criteria:

- results in death,
- is life threatening (the patient was at risk of death at the time of the event; it does NOT refer to an event which hypothetically might have caused death if it were more severe),
- requires in-patient hospitalisation or prolongation of existing hospitalisation - hospitalisation required by the study will not be considered as an AE,
- results in persistent or significant disability/incapacity (substantial disruption of a person's ability to carry out normal life functions),
- is a congenital anomaly/birth defect,
- is any important medical event that may not be immediately life threatening or result in death or hospitalisation but, based upon appropriate medical judgment, may endanger the patient or may require intervention to prevent one of the other outcomes listed in the definition above, and should also be reported in the same way as an SAE. Examples of such events are invasive or malignant cancers, intensive treatment in an emergency room or at home for allergic bronchospasm, blood dyscrasias or convulsions that do not result in hospitalisation; or development of drug dependency or drug abuse.

Distinction should be made between serious and severe AEs. Severity is a measure of intensity whereas seriousness is based on the outcome or the action criteria described above, for example, nausea that persists for several hours may be considered as severe, but not as an SAE. On the contrary, a cardiovascular event that causes limited degree of disability may be considered as not severe but would be recorded as an SAE.

- Events initially reported as an AE may become serious. For example, diarrhoea may become debilitating and require hospitalisation or prolongation of hospitalisation and is then reported as an SAE.
- Surgical intervention is not to be considered as a SAE but the medical condition requiring the surgery is to be reported as such.
- If a medical condition known before the start of study treatment requires hospitalisation for planned surgical measures, it should not be considered as an AE. However, the medical condition should be reported in the medical history.
- Occurrence of study drug misuse/abuse, overdose or drug dependency, whether or not associated to an adverse event, must be recorded, reported immediately to the Sponsor.

### **9.5.2. Definition of Specific Events in the Study (if applicable)**

A worsening of the CIDP will not be regarded as an AE (or a SAE) and will be recorded in specific eCRF forms. These data will be analysed as part as the efficacy assessment.

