### **9.5.3. Adverse Event Recording and Reporting**

#### **Period of (Serious) Adverse Event Data Collection:**

In order to ensure complete safety data collection, recording and reporting, all (S)AEs occurring during the study, i.e. after signature of the Informed Consent, must be recorded, even if no study drug was administered. These include all AEs occurring, recurring, or worsening after the signature

of the informed consent. The period of observation for the study is from the screening visit to the visit.

An AE occurring between signature of PRISM 2 Informed consent and first study drug administration will be considered as TEAE of PRISM - I10E-1302.

If the Investigator becomes aware, after that period, of any unusual safety information or any safety information that appears to be drug related involving a patient who had participated in the study, even after the patient completes the study, he/she should contact the sponsor to determine how it should be documented and reported.

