### **Recording and Description of (Serious) Adverse Event:**

All AEs occurring after signature of the informed consent until the visit will be recorded in the appropriate pages of eCRF, including AEs occurring during the screening period and before the first administration of study drug, other than baseline findings which will be recorded as medical history.

Each individual AE is to be listed as a separate entry on the AE e-CRF form. The Investigator will provide information on dates of onset and resolution, seriousness, severity, frequency, action(s) taken with regard to corrective therapy or to the study drug, outcome and relationship to the study drug. The Investigator must report to the Sponsor or its designee all AEs that occur during the study from the time the written informed consent is given until the EOS visit or premature termination, regardless of their relationship to the study drug. Apart from AEs clinically observed by the Investigator, the patient will be given the opportunity to report AEs spontaneously. A general prompt will also be given to detect AEs, e.g. "Did you experience any illness or unusual symptom since your last visit?"

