### **Follow-up of Adverse Events:**

All AEs or SAEs assessed as not related to study medication, including clinically significant laboratory tests or physical examination findings, must be followed until the event resolves, the condition stabilizes, the event is otherwise explained, or the final study visit occurs, whichever comes first.

AEs or SAEs assessed as related to study drug will be followed for as long as necessary to adequately evaluate the subject's safety, or until the event stabilizes, or the subject is lost to follow up. If resolved, a resolution date should be provided.

The Investigator is responsible for ensuring that follow-up includes any supplemental investigations indicated to elucidate the nature and/or causality of the AE. This may include additional clinical laboratory testing or investigations, histopathological examinations, or consultation with other health care professionals as is practical.

If a patient is withdrawn from study due to safety reasons, he/she should be followed until the event disappears, is otherwise explained or the patient's condition has stabilised.

Any patient who voluntarily withdraws from the study should be carefully questioned for the possible occurrence of an adverse event. Whenever possible, a patient should be followed through the last scheduled visit.

If no follow-up information can be provided after all efforts and attempts, the Investigator must document the outcome as “unknown” and provide a justification.

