#### **9.5.4. Procedures for Reporting Serious Adverse Events, Pregnancy and Overdose/Abuse/Misuse**

##### **9.5.4. 1. SAE**

The Sponsor or its representative must be informed immediately, and no later than 24 hours, of receipt of the SAE information by the site.

If one or more seriousness criteria is fulfilled, the Investigator must promptly forward to the Sponsor or its representative a duly completed “SERIOUS ADVERSE EVENT NOTIFICATION FORM” provided by the Sponsor, even if the data are incomplete or if it is obvious that more data will be needed in order to draw any conclusions, but as soon as the minimum of following information is present:

- identification of the notifying person,
- identification of the clinical study,
- identification of a patient (patient number and/or initials),
- description of the SAE and relationship to the study drug.

After the initial SAE report, the Investigator is required to proactively follow each patient and to provide further information on the patient’s condition. The Investigator will ensure that follow-up includes any further investigations as may be indicated to elucidate the nature or the causality of the SAE.

Supporting documentation (discharge summaries, all examinations carried out, etc.) will not be sent systematically, as all relevant information must appear and be summarized in the narrative of the SAE report. However, if judged important, the Investigator could send these documents or LFB could request them (all documents must be blinded with respect to the subject’s name). Any follow-up information must be reported within the same timelines.

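### Protocol 9.5.2 exempts all CIDP worsening from AE and SAE status, so a fatal, life-threatening or hospitalised worsening triggers no 24-hour report and cannot enter the SAE outputs

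*Protocol*

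**What the plan says.** Protocol 9.5.1 gives the general rule. Among the things that may be an AE it lists "The deterioration of a pre-existing chronic disease or aggravation of a symptom or disease that was present at inclusion". It then defines a serious AE as an AE that meets at least one criterion. The criteria include death, life threat and an event that "requires in-patient hospitalisation or prolongation of existing hospitalisation".

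Protocol 9.5.2 makes a specific exemption from that rule: "A worsening of the CIDP will not be regarded as an AE (or a SAE) and will be recorded in specific eCRF forms". The data are then analysed with efficacy. No level of seriousness is carved out.

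Protocol 9.5.4.1 sets the expedited duty: "The Sponsor or its representative must be informed immediately, and no later than 24 hours, of receipt of the SAE information by the site".

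Protocol 3.1.6 defines relapse in two ways. One is a rise of 1 point in adjusted INCAT with a treatment change that the investigator considers mandatory. The other is a rise of at least 2 points. Relapsing patients are withdrawn.

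SAP 4.7.2 derives and summarises seriousness for AEs and does not mention CIDP worsening. SAP 4.1 requires a listing of every discontinued patient with the reason and the investigator's specifications.

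**The concern.** Safety is the secondary objective (Protocol 2.2). Protocol 1.4 says that the reduced dose of 0.5 g/kg is tested to document its effect on relapse in patients previously maintained on 1 g/kg. Relapse is therefore the harm most directly tied to the dose under study. Protocol 3.4 sets up no DSMB, and SAP 4.10 reports that the study was ended early because of relapse.

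If a relapse put a patient in hospital, a site following the plan would complete the worsening form and withdraw the patient, but would send no SAE report. A reader of the safety results would learn how many patients relapsed and when. No specified output would say whether those relapses were handled as outpatients or led to admission, a life-threatening course or death.

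**Working it through.** The plan states no figure on this point, so the check sets the sections side by side.

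**Step 1: status.** A serious AE is by definition an AE (9.5.1). Worsening of CIDP is not an AE (9.5.2). So worsening of CIDP cannot be an SAE, whatever its consequence.

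**Step 2: reporting.** The duty in 9.5.4.1 starts with SAE information, so it never starts for a worsening. Section 9.5.3 has a route for unusual safety information, under which "he/she should contact the sponsor to determine how it should be documented and reported". It applies only after the observation period. Worsening found at a visit reaches the eCRF, to be completed within 5 days of the visit (11.1.2.4). That clock runs from the visit and the 24 hours run from receipt at the site, so the two are not directly comparable.

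**Step 3: data.** Seriousness is specified as a field of the AE record (9.5.3): "The Investigator will provide information on dates of onset and resolution, seriousness, severity, frequency, action(s) taken". The content of the worsening forms is not described, so they may or may not hold it.

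**Step 4: outputs.**

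| Output | What it shows of a worsening | Requires death, life threat or hospitalisation? |
|---|---|---|
| Responder rate at EOS (SAP 4.6.1) | Non-response | No |
| Adjusted INCAT, R-ODS (SAP 4.6.2) | Size of the score change | No |
| Time to relapse (SAP 4.6.2) | Number and timing | No |
| Withdrawal for insufficient response (SAP 4.1) | Basis for the judgement, follow-up treatment | No |
| Discontinuation listing, mandatory (SAP 4.1) | Reason, investigator's specifications | No, though the specifications may mention it |
| In-text listing, optional (SAP 4.1) | Relapse risk information | No |
| Seriousness summary, SAE tables and listing (SAP 4.7.2) | Nothing, as they draw on AE records | Yes, for AEs only |

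**Step 5: workload.** Inputs are 15 to 30 patients (Protocol 12.3) and 24-week relapse of 13% at 1 g/kg and 45% on placebo in the trial cited in Protocol 1.1.2. Assumptions: relapse at 0.5 g/kg lies between those two rates, the relapse definitions are comparable, and follow-up is complete.

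- Week 24, n × p: 15 × 0.13 = 1.95 and 30 × 0.45 = 13.5, so about 2 to 14 relapses.
- Week 48 at constant hazard, n × [1 − (1 − p)²]: 1 − 0.87² = 24.3% and 1 − 0.55² = 69.8%. Then 15 × 0.243 = 3.6 and 30 × 0.698 = 20.9, so about 4 to 21 relapses.

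The documents give no share s of relapses that are serious. If s were 5% to 25%, the chance of at least one by week 24, 1 − (1 − p × s)ⁿ, would run from 1 − (1 − 0.13 × 0.05)¹⁵ = 9% to 1 − (1 − 0.45 × 0.25)³⁰ = 97%. A range that wide settles nothing about the number of serious cases.

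**The case against.** Sending an efficacy event to the efficacy analysis is a deliberate and reasonable choice, and 9.5.2 is a specific rule that overrides the general one rather than a contradiction of it. Relapse is defined by a rise in disability, with or without a mandatory treatment change. Many ordinary relapses could therefore be argued to meet the disability criterion, or to be an important medical event that "may endanger the patient or may require intervention to prevent one of the other outcomes listed in the definition above". Making every such relapse an SAE would largely undo the exemption. This objection stands, and it limits any exception to death, life threat and unplanned hospitalisation.

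Three stronger readings are tempting, and the documents do not support them.

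- *That worsening goes unreported.* It does not. INCAT is scored at every visit, every relapser should be withdrawn, and so every relapser should appear in the mandatory discontinuation listing. A death could be entered there under the category for other reasons. Complications that are separate events, such as a fall or an infection, remain reportable as AEs or SAEs.
- *That a serious relapse made an SAE would still lack follow-up.* A reader might infer this from 9.5.3, where unrelated events "must be followed until the event resolves, the condition stabilizes, the event is otherwise explained, or the final study visit occurs, whichever comes first". But 5.4 requires a patient withdrawn because of an AE to be followed to resolution or stabilisation, and 9.5.3 says much the same for withdrawal on safety grounds. No separate follow-up rule is needed.
- *That 2 to 14 or 4 to 21 counts the missing cases.* Those figures count all relapses, which SAP 4.6.2 already reports.

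It is also fair to say that no efficacy estimate changes, that the relapse signal was detected, and that the study was stopped because of it.

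**Conclusion.** The point holds in a narrow form. As written, 9.5.2 leaves a fatal, life-threatening or hospitalised worsening of CIDP without a 24-hour report and outside the seriousness summaries and SAE tables. The efficacy and disposition outputs show that the worsening happened, but none is required to show how serious it was. The investigator's specifications in the discontinuation listing might reveal a serious case, but nothing makes them do so.

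The importance is minor to modest and concerns mainly the completeness of the safety report. It does not touch the relapse rate or the primary endpoint. The number of cases affected cannot be derived from the documents and may be zero. The conclusion rests on the text available; the worsening forms are not described and could already hold the needed data, which would make the fix easier.

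**What to change.** **1. SAP, before database lock.** Add a column to the mandatory discontinuation listing in SAP 4.1 showing whether the CIDP worsening resulted in death, was life-threatening or required unplanned hospitalisation. Beside the SAE summary in SAP 4.7.2, and kept separate from it, give the number and percentage of TTS patients with such worsening. Label it as a retrospective review by the study physician, and mark patients without the necessary records as not assessable. SAP 4.6.1 already uses study-physician review before lock to flag corticosteroid and immunosuppressant records. That task is simpler than judging seriousness, but the mechanism exists.

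**2. Protocol 9.5.2, for any patient still on study.** Add:

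> Worsening of CIDP that results in death, is life-threatening or requires unplanned in-patient hospitalisation is also reported as an SAE under 9.5.4.1; other worsening remains exempt.

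**Cost.** One protocol sentence, one listing column, one count with its percentage, and a review of at most about 4 to 21 relapses under the assumptions above. Serious relapses will appear in both efficacy and safety outputs, which the separate display makes clear. The review is made after the relapse results are known; confining it to three concrete consequences limits the room for judgement. Early termination leaves part 2 with little prospective effect, so most of the value lies in part 1.

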### **9.5.3. Adverse Event Recording and Reporting**

#### **Period of (Serious) Adverse Event Data Collection:**

In order to ensure complete safety data collection, recording and reporting, all (S)AEs occurring during the study, i.e. after signature of the Informed Consent, must be recorded, even if no study drug was administered. These include all AEs occurring, recurring, or worsening after the signature

of the informed consent. The period of observation for the study is from the screening visit to the visit.

An AE occurring between signature of PRISM 2 Informed consent and first study drug administration will be considered as TEAE of PRISM - I10E-1302.

If the Investigator becomes aware, after that period, of any unusual safety information or any safety information that appears to be drug related involving a patient who had participated in the study, even after the patient completes the study, he/she should contact the sponsor to determine how it should be documented and reported.

### **Recording and Description of (Serious) Adverse Event:**

All AEs occurring after signature of the informed consent until the visit will be recorded in the appropriate pages of eCRF, including AEs occurring during the screening period and before the first administration of study drug, other than baseline findings which will be recorded as medical history.

Each individual AE is to be listed as a separate entry on the AE e-CRF form. The Investigator will provide information on dates of onset and resolution, seriousness, severity, frequency, action(s) taken with regard to corrective therapy or to the study drug, outcome and relationship to the study drug. The Investigator must report to the Sponsor or its designee all AEs that occur during the study from the time the written informed consent is given until the EOS visit or premature termination, regardless of their relationship to the study drug. Apart from AEs clinically observed by the Investigator, the patient will be given the opportunity to report AEs spontaneously. A general prompt will also be given to detect AEs, e.g. "Did you experience any illness or unusual symptom since your last visit?"

### **Follow-up of Adverse Events:**

All AEs or SAEs assessed as not related to study medication, including clinically significant laboratory tests or physical examination findings, must be followed until the event resolves, the condition stabilizes, the event is otherwise explained, or the final study visit occurs, whichever comes first.

AEs or SAEs assessed as related to study drug will be followed for as long as necessary to adequately evaluate the subject's safety, or until the event stabilizes, or the subject is lost to follow up. If resolved, a resolution date should be provided.

The Investigator is responsible for ensuring that follow-up includes any supplemental investigations indicated to elucidate the nature and/or causality of the AE. This may include additional clinical laboratory testing or investigations, histopathological examinations, or consultation with other health care professionals as is practical.

If a patient is withdrawn from study due to safety reasons, he/she should be followed until the event disappears, is otherwise explained or the patient's condition has stabilised.

Any patient who voluntarily withdraws from the study should be carefully questioned for the possible occurrence of an adverse event. Whenever possible, a patient should be followed through the last scheduled visit.

If no follow-up information can be provided after all efforts and attempts, the Investigator must document the outcome as “unknown” and provide a justification.

